**PROTOCOL REFERENCE information**

Title	Clinical course, outcomes and risk factors of myocarditis and pericarditis following administration of Moderna vaccines targeting SARS-CoV-2.
Protocol version identifier	4.0
Current date of the protocol	24 January 2024
EU PAS register number	EUPAS105009
International non-proprietary name (INN)	Moderna vaccines targeting SARS CoV-2 (Elasomeran, elasomeran/imelasomeran, elasomeran/davesomeran)
Medicinal product	Spikevax, Spikevax bivalent
Product reference	EMA/H/C/005791
Procedure number	MEA 0065 – P910
Marketing authorisation holder(s)	European Union: Moderna Biotech Spain, S.L. [name]
Joint PASS	No
Research question and objectives	
The overarching goal of this study is to describe the clinical course, outcomes and risk factors for myocarditis and pericarditis associated with Moderna vaccination targeting SARS-CoV-2.
 
This study plans to investigate the natural course in terms of morbidity and to identify the relevant prognostic factors using the following study objectives.
 
Primary objectives:
 
1 To identify possible risk factors for myocarditis and pericarditis following Moderna vaccination targeting

	
SARS-CoV-2, including demographic characteristics, medical history, and vaccination characteristics.
 
2. To characterize the clinical course of myocarditis and pericarditis of varying origin, including myocarditis and pericarditis associated with Moderna vaccination targeting SARS-CoV-2, and myocarditis or pericarditis not associated with vaccinations targeting SARS-CoV-2, and to identify prognostic factors in the course of myocarditis and pericarditis.
 
Secondary objectives:
 
1. To identify whether there are differences in the clinical course and risk factors between myocarditis and pericarditis associated with Moderna vaccination targeting SARS-CoV-2, and myocarditis and pericarditis not associated with vaccinations targeting SARS-CoV-2.
 
2. If severe cases or cases with sequelae are identified, to identify risk factors for severe myocarditis and pericarditis associated with Moderna vaccination targeting SARS-CoV-2.

Countries of study
	
Four countries (Denmark, Norway, Spain, United Kingdom).

## 2. List of abbreviations

Abbreviation	Explanation
ACCESS	vACCine COVID-19 monitoring readinESS
AESI	Adverse event of special interest
ATC	Anatomical Therapeutic Chemical
CCI	Charlson Comorbidity Index
CDC	Centers for Disease Control and Prevention
CDM	Common data model
CI	Confidence interval
COVID-19	Coronavirus disease 2019
CPRD	Clinical Practice Research Datalink
DAP	Database access provider
DSRU	Drug Safety Research Unit
ECMO	Extracorporeal membrane oxygenation
EEA	European Economic Area
EMA	European Medicines Agency
ENCePP	European Network of Centres for Pharmacoepidemiology and Pharmacovigilance
EU	European Union
EEA	European Economic Area
GDPR	General Data Protection Regulation
GVP	Guideline on good pharmacovigilance practices
HR	Hazard ratio
ICD-9CM	International Classification of Diseases, 9th Revision, Clinical Modification
ICD-10CM	International Classification of Diseases, 10th Revision, Clinical Modification
ICD-10	International Classification of Diseases, 10th Revision
ICPC	International Classification of Primary Health Care
ICU	Intensive care unit
IVIG	Intravenous immunoglobulins
MAH	Marketing Authorisation Holder
mRNA	Messenger ribonucleic acid
OR	Odds ratio
PASS	Post-authorisation safety study
PRAC	Pharmacovigilance Risk Assessment Committee
RMP	Risk Management Plan
SAP	Statistical Analysis Plan
SARS-CoV-2	severe acute respiratory syndrome coronavirus 2

Abbreviation	Explanation
SE	Standard error
SNOMED	Systematised Nomenclature of Medicine
STROBE	Strengthening the Reporting of Observational Studies in Epidemiology
TVEM	Time-varying effect model
UK	United Kingdom
US	United States
VAC4EU	Vaccine Monitoring Collaboration for Europe
WHO	World Health Organisation

## 4. Abstract

**Title:** Clinical course, outcomes and risk factors of myocarditis and pericarditis following administration of Moderna vaccines targeting SARS-CoV-2.

**Short title:** Myocarditis and pericarditis after mRNA-1273

**Protocol date & version:** 24 January 2024, version 4.0

**Coordinating investigator:** [name], Julius Clinical, the Netherlands

### Rationale and background

The severe acute respiratory syndrome coronavirus 2 (SARS-CoV-2) causes coronavirus disease 2019 (COVID-19) and has led to a global pandemic. A mass vaccination campaign has been implemented in Europe. The mRNA-1273 vaccine, currently known as Elasmomeran, and the more recent omicron-containing bivalent booster vaccine, currently known as imelasomeran, combine Moderna's mRNA (messenger ribonucleic acid) delivery platform with the stabilised SARS-CoV-2 spike immunogen.

Cases of myocarditis and pericarditis have been observed following vaccination with mRNA vaccines targeting SARS-CoV-2, including Elasmomeran. Most of these cases have occurred within 14 days following vaccination, more often after the second dose and in younger men aged 18 to 39. This increased risk has been described in several observational studies to date. Although most cases of vaccine-associated myocarditis and pericarditis have been described as mild, additional data are needed to document the inflammation's clinical course and longer-term outcomes of these events. Follow-up research can also serve to identify possible risk factors for both the occurrence and severity of myocarditis and pericarditis.

### Research question and objectives

The overarching goal of this study is to describe the clinical course, outcomes and risk factors for myocarditis and pericarditis associated with Moderna vaccination targeting SARS-CoV-2. We will investigate the clinical course in terms of morbidity and to identify the relevant prognostic factors using the following study objectives:

#### Primary objectives:

1. To identify possible risk factors for myocarditis and pericarditis following Moderna vaccination targeting SARS-CoV-2, including demographic characteristics, medical history, and vaccination characteristics.
2. To characterize the clinical course of myocarditis and pericarditis of varying origin, including myocarditis and pericarditis associated with Moderna vaccination targeting SARS-CoV-2, and myocarditis or pericarditis not associated with vaccinations targeting

SARS-CoV-2, and to identify prognostic factors in the course of myocarditis and pericarditis.

**Secondary objectives:**

1. To identify whether there are differences in the clinical course and risk factors between myocarditis and pericarditis associated with Moderna vaccination targeting SARS-CoV-2, and myocarditis and pericarditis not associated with vaccinations targeting SARS-CoV-2.
2. If severe cases or cases with sequelae are identified, to identify risk factors for severe myocarditis and pericarditis associated with Moderna vaccination targeting SARS-CoV-2.

**Study design:**

The study will include two distinct designs to answer the primary and secondary objectives.

Case Cohort: To assess risk factors for development of post-vaccine myocarditis and pericarditis, a case-cohort of recipients of Moderna vaccination targeting SARS-CoV-2 will be defined in each participating database. This set will be used to investigate the first primary objective.

The Case-Cohort design requires (1) all cases of myocarditis and pericarditis who previously had received Moderna vaccination targeting SARS-CoV-2 (2) a random subsample of the original cohort ('subcohort'), selected independently of the definition of cases.

Cohort: To characterize the clinical course, outcomes, and risk factors for severe disease, a cohort of myocarditis cases (with and without prior exposure to Moderna vaccination targeting SARS-CoV-2) will be studied. Severe disease will be a composite endpoint based on the diagnosis of acute coronary syndrome, acute myocardial infarction, heart failure, atrial fibrillation/flutter, ventricular arrhythmias/cardiac arrest, pulmonary embolism or deep venous thrombosis, stroke outcomes, peripheral arterial embolism, hospital readmission, Intensive Care Unit (ICU) admission or death.

The cohort set will be used to investigate the second primary objective and both secondary objectives.

**Population:**

For the case-cohort design, the cohort is the group of individuals with at least one dose of a Moderna vaccination targeting SARS-CoV-2. Inclusion criteria are at least one year of enrolment in the applicable database prior to the index vaccine dose and without myocarditis events within 6 months prior to receiving a Moderna vaccination targeting SARS-CoV-2. Cases are individuals meeting the criteria of myocarditis or pericarditis. Moreover, cases should be able to meet the adjudication criteria according to the Brighton Collaboration Case Definition for possible, probable, or definite myocarditis or pericarditis.

For the cohort design, individuals meeting the criteria of myocarditis or pericarditis, with at least one year of enrolment in the applicable database prior to the index myocarditis or pericarditis event will be included. Cases of myocarditis and pericarditis will be excluded if these individuals have no record of a Moderna vaccine targeting SARS-CoV-2 but a record of another vaccine targeting SARS-CoV-2 within 30 days prior to the onset of myocarditis or pericarditis. Within the cohort design, all cases following vaccination are adjudicated according to the Brighton Collaboration Case Definition. A 1:1 matched sample of the cases not following vaccination matched based on sex and age will also be adjudicated. Only cases that meet the adjudication criteria for possible, probable, or definite myocarditis or pericarditis are included.

### Endpoints:

Objective	Endpoint	Analysis Set
Primary		
To identify possible risk factors for myocarditis and pericarditis post-Moderna vaccination targeting SARS-CoV-2, including demographic characteristics, medical history, and vaccination characteristics.	Myocarditis or pericarditis within 30 days after Moderna vaccination targeting SARS-CoV-2.	Case-cohort
To characterize the clinical course of myocarditis and pericarditis of varying origin, including myocarditis and pericarditis associated with Moderna vaccination targeting SARS-CoV-2, and myocarditis or pericarditis not associated with vaccinations targeting SARS-CoV-2, and to identify prognostic factors in the course of myocarditis and pericarditis.	
Clinical outcomes within 30 days of myocarditis' or pericarditis' onset,
 
 
• Acute coronary syndrome or acute myocardial infarction;
 
• Heart failure;
 
• Atrial fibrillation/flutter;
 
• Ventricular arrhythmias/cardiac arrest;
 
• Pulmonary embolism or deep venous thrombosis;
 
• Stroke outcomes;
 
• Peripheral arterial embolism;
 
• Hospital readmission;
 
• ICU admission; and/or
 
• Death.
 
 
Long term outcome (90 day, 6 months or 12 months depending on availability of data),:
	Cohort

	
 
• Acute coronary syndrome or acute myocardial infarction;
 
• Heart failure;
 
• Atrial fibrillation/flutter;
 
• Ventricular arrhythmias/cardiac arrest;
 
• Pulmonary embolism or deep venous thrombosis;
 
• Stroke outcomes;
 
• Peripheral arterial embolism;
 
• Hospital readmission;
 
• ICU admission; and/or
 
• Death.
 
	

Secondary
		

To identify whether there are differences in the clinical course and risk factors between myocarditis and pericarditis associated with Moderna vaccination targeting SARS-CoV-2, and myocarditis and pericarditis not associated with vaccinations targeting SARS-CoV-2.
	
Clinical outcomes within 30 days of myocarditis' or pericarditis' onset,:
 
 
• Acute coronary syndrome or acute myocardial infarction
 
• Heart failure
 
• Atrial fibrillation/flutter
 
• Ventricular arrhythmias/cardiac arrest
 
• Pulmonary embolism or deep venous thrombosis
 
• Stroke outcomes
 
• peripheral arterial embolism
 
• Hospital readmission
 
• ICU admission
 
• Death
 
 
Long term outcome (90 day, 6 months or 12 months depending on availability of data:
 
 
• Acute coronary syndrome or acute myocardial infarction;
 
• Heart failure;
 
• Atrial fibrillation/flutter;
 
• Ventricular arrhythmias/cardiac arrest;
 
	
Cohort

	
 
• Pulmonary embolism or deep venous thrombosis;
 
• Stroke outcomes;
 
• Peripheral arterial embolism;
 
• Hospital readmission;
 
• ICU admission; and/or
 
• Death.
 
	
If severe cases or cases with sequelae are identified, to identify risk factors for severe myocarditis and pericarditis associated with Moderna vaccination targeting SARS-CoV-2.	Severe myocarditis or pericarditis within 30 days after Moderna vaccination targeting SARS-CoV-2, as well as severe myocarditis or pericarditis in the longer term.	Cohort

### Variables:

**Exposures:** The main variable of interest is vaccination with any dose of Moderna vaccination targeting SARS-CoV-2. In both the Moderna vaccination-exposed case-cohort analysis and the myocarditis/pericarditis cohort, myocarditis and pericarditis cases (each separately) will be described as recently exposed to Moderna vaccination targeting SARS-CoV-2 if at least one dose of a Moderna vaccine was received within 30 days prior to the onset of myocarditis/pericarditis. Individuals with exposure more than 30 days prior to onset of myocarditis/pericarditis will be considered to have past exposure, and individuals with no history of Moderna vaccination targeting SARS-CoV-2 will be considered unexposed.

**Outcomes:** Myocarditis and pericarditis cases will be confirmed based on adjudication criteria according to the Brighton Collaboration Case Definition. Possible, Probable and Definite cases will be included. If feasible, cases with a severe clinical course or long-term sequelae will be identified as a subgroup analysis. **Covariables:** Risk factors will be explored, including demographic characteristics (e.g., age, sex, geography), lifestyle factors (e.g., tobacco use, substance use, level of physical activity), medical history (including chronic conditions, recent acute events such as infection including COVID-19, cardiac history), and recent medication/vaccination use.

For cases following administration of Moderna vaccination targeting SARS-CoV-2, characteristics of vaccination will also be explored, including: product, dosing interval; dose number; primary series versus booster dose; homologous versus heterologous schedule; and, co-administration with other vaccines.

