## **9. Research methods**

### **9.1 Study design**

To answer the objectives, this study will use an Moderna vaccination targeting SARS-CoV-2-exposed case-cohort design and a myocarditis cohort study design (Figure 1).

The case-cohort design will be used to assess risk factors other than Moderna vaccination targeting SARS-CoV-2 for the development of myocarditis and pericarditis in recipients of the Moderna vaccine targeting SARS-CoV-2, to understand which characteristics increase or decrease the risk for the development of myocarditis and pericarditis after vaccination (i.e., t0). This may contribute to risk assessment and identification of individuals who do not have an increased risk on myocarditis or pericarditis.

[figure not shown]
The cohort design will be used to describe prognostic factors for a (severe) clinical course in patients with myocarditis or pericarditis regardless of vaccination status. As most myocarditis and pericarditis cases are mild in disease severity, it is clinically relevant to identify the individuals who are at increased risk for severe clinical outcomes as early as possible, in order to provide appropriate care in a timely manner. These severe outcomes are acute coronary syndrome, acute myocardial infarction, heart failure, atrial fibrillation/flutter, ventricular arrhythmias/cardiac arrest, pulmonary embolism or deep venous thrombosis, stroke outcomes, peripheral arterial embolism, hospital readmission, ICU admission or death. Therefore, information available at the onset of myocarditis or pericarditis (i.e., t1) could be used to predict the clinical course including long-term outcomes (i.e., t2).

The cohort design will also be used to address both secondary study objectives. Within the cohort of myocarditis/pericarditis cases, clinical course and risk profiles will be compared between patients with myocarditis/pericarditis recorded after vaccination targeting SARS-CoV-2 and patients with myocarditis/pericarditis unrelated to vaccine administration. Moreover, risk factors for severe myocarditis/pericarditis will be investigated within this cohort.

Recipients of Moderna vaccination targeting SARS-CoV-2 and cases of myocarditis and pericarditis will be identified between January 2021 (date of the earliest approval of Moderna vaccines targeting SARS-CoV-2 in Europe) and the end of the study period (defined as most recent data availability at the time of the End of Data collection).

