### **9.3.4 Subgroups**

The feasibility of performing subgroup analyses will be strongly driven by available sample size.

In the case-cohort design a subgroup analysis will be performed in the following subgroups: young children (<12 years), adolescents (12-17 years), young adults (18-24 years), male and female.

In the cohort design of all myocarditis/pericarditis cases, a subgroup analysis will be performed in the following subgroups: Moderna vaccination targeting SARS-CoV-2-exposure status (Recently exposed, Past exposure, Never exposed), SARS-CoV-2 infection status (Recent infection, Past infection, Never infected) prior to myocarditis/pericarditis onset.

As feasible, stratified analyses by different variants of the Moderna vaccine targeting SARS-CoV-2 will be presented for both the case-cohort and the cohort designs. First, descriptive analyses in the above subgroups will be presented. Subsequent multivariable analyses will only be performed in subgroups that are sufficiently large in size. Details will be further elaborated in the SAP.

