### Cohort analysis

To identify differences in clinical course (Primary objective 2) and differences in risk factors (Secondary objective 1) for vaccine associated myocarditis/pericarditis and vaccine unrelated myocarditis/pericarditis, cases in the cohort analysis will be compared based on vaccination status. Outcomes and identified follow-up care will also be characterized, where feasible. If sequelae or unusually severe cases are identified, cases with and without sequelae will be compared.

Standard descriptive statistics (see [Section 9.7](#)) will be used to characterise clinical course, outcomes, and long-term outcomes following the initial myocarditis/pericarditis episode. Cox regression analysis will be utilized to compare the presence of sequelae following myocarditis/pericarditis (e.g., death, subsequent cardiovascular events, cardiac hospitalizations) between recent Moderna vaccination targeting SARS-CoV-2-exposed and unexposed cases as feasible.

If myocarditis and pericarditis cases with severe presentation or long-term sequelae are identified, a similar modelling approach for the cohort design will be applied to explore applicable risk factors as feasible (Secondary objective 2). Candidate risk factors will be selected using a two-step variable selection method: starting with a univariate approach for the selection of relevant variables, and followed by a stepwise backward variable selection approach.

The analysis will be performed per DAP (i.e., models will be trained locally for each DAP), and results will be presented on DAP level. The parameter estimate, SE, and hazard ratio (HR) for each model parameter will be presented together with its 95% CI.

Further details on all analyses can be found in the SAP.

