### 9.7.3 Subgroup analyses

Descriptive statistics will be presented for the subgroups as defined in [Section 9.3.4](#). Statistical analyses on subgroups will be considered only if feasible based on available sample size.

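### The risk-factor part of secondary objective 1 rests on a case-to-case comparison that leaves past-exposed cases unassigned, and against never-Moderna cases it would mix a factor's effect with who received Moderna

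*Protocol*

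**What the plan says.** The objective is "To identify whether there are differences in the clinical course and risk factors between myocarditis and pericarditis associated with Moderna vaccination targeting SARS-CoV-2" and cases not associated with vaccination. The protocol assigns it to the cohort design, which contains cases only (Abstract, Study design and Endpoints; section 9.1.2; Table 1).

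Three exposure classes are defined in the Abstract (Variables) and section 9.3.1. Recent means a Moderna dose within 30 days before onset. For the second class, "Individuals with exposure more than 30 days prior to onset of myocarditis/pericarditis will be considered to have past exposure". For the third, "individuals with no history of Moderna vaccination targeting SARS-CoV-2 will be considered unexposed".

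Section 9.7.2 (Cohort analysis) covers clinical course and risk factors in one sentence: "cases in the cohort analysis will be compared based on vaccination status". The comparator class is not named. Section 9.1 describes the comparators as "patients with myocarditis/pericarditis unrelated to vaccine administration", which does not place past-exposed cases either. The one model contrast with named groups is the Cox comparison of sequelae, "between recent Moderna vaccination targeting SARS-CoV-2-exposed and unexposed cases as feasible". Past-exposed cases are in neither group of that contrast.

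Section 9.3.4 lists recent, past and never exposed as cohort subgroups. They are descriptive first, and section 9.7.3 adds that "Statistical analyses on subgroups will be considered only if feasible based on available sample size".

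Comparator cases are sampled 1:1, matched on age and sex (section 8.2). Section 9.9 plans multivariable adjustment as feasible. It expects no threat from selection bias, on the ground that the databases represent the background population.

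**The concern.** In a comparison confined to cases, a factor can differ between groups for two reasons. It may act differently in the two kinds of disease, which is what the objective asks. Or it may be more or less common among people given Moderna than among people who never had it. Comorbidity, frequency of health-care contact and membership of a priority group are plausible examples.

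Matching removes the second reason for age and sex only. Adjustment can remove the part of the association with receipt that runs through other measured variables. It cannot remove the factor's own direct link with receipt, because that factor is the quantity being compared. How well a database represents its population, the argument in section 9.9, does not bear on who within it received Moderna.

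At stake is a reported difference in risk factors where none exists, or a real one that is masked. Past-exposed cases come from the recipient population, so they are the natural check. The plan gives them no role in this comparison.

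**Working it through.** **Group sizes in the protocol.** Section 9.5 expects 20-80 myocarditis and 50-140 pericarditis cases per data access provider (DAP) in the case-cohort. It gives the cohort as 40-160 and 100-280, which the Abstract labels per DAP.
- 2 x 20 = 40 and 2 x 80 = 160
- 2 x 50 = 100 and 2 x 140 = 280

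The cohort sizes are exactly twice the post-vaccine numbers. That fits two 1:1 groups and shows no separate number for past-exposed cases. I use 20 and 80 per group below.

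**Formula.** Let pV and pN be the prevalence of a factor among Moderna recipients and never-Moderna people, and RR_V and RR_N its risk ratio in each. The odds of the factor among cases are p x RR / (1 - p), so

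case-case OR = (RR_V / RR_N) x [pV/(1 - pV)] / [pN/(1 - pN)].

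The first term is what the objective asks. The second is the factor's odds ratio for Moderna receipt.

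**No true difference (RR 2 in both groups; all prevalences assumed).**
- pV 0.20, pN 0.10: (0.25 x 2) / (0.1111 x 2) = 2.25. The factor is present in 33.3% versus 18.2% of cases.
- pV 0.20, pN 0.15: (0.25 x 2) / (0.1765 x 2) = 1.42. The factor is present in 33.3% versus 26.1% of cases.

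**True twofold difference (RR 4 versus 2), factor half as common in recipients (pV 0.10, pN 0.20).**
- (0.1111 x 4) / (0.25 x 2) = 0.89, so the difference is masked.

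**How often a 95% Wald interval excludes 1 with no true difference.** For OR 2.25 and 80 per group the expected cells are 26.7, 53.3, 14.5 and 65.5.
- SE = sqrt(1/26.7 + 1/53.3 + 1/14.5 + 1/65.5) = 0.37
- z = ln(2.25)/0.37 = 2.17
- Probability about 0.58

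| Case-case OR | 20 per group | 80 per group |
|---|---|---|
| 1.42 | 8% | 17% |
| 2.25 | 19% | 58% |

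The bias in the estimate does not depend on the number of cases. Only the chance of declaring it significant does.

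**Against past-exposed cases.** Assume the factor is equally common among recipients in both time windows, and that late-onset disease in recipients has the same factor effect as in never-Moderna people. The second term is then 1, and the expected ORs are 1.0 (no true difference) and 2.0 (twofold difference).

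**The case against.** **The protocol does not fix never-Moderna as the risk-factor comparator.** Correct. A reader might infer that vaccine-associated cases are contrasted only with never-Moderna cases, but the documents do not support that. The named contrast is for sequelae, the risk-factor comparator is left open, and section 9.3.4 plans a recent/past/never display. For primary objective 1 the controls are themselves Moderna recipients (section 9.1.1). The SAP, which is not at hand, may settle the comparator. What remains is that the protocol assigns this objective to a case-to-case comparison in which a defined class has no place. The conditional subgroup display gives the objective no contrast.

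**Adjustment helps.** In part. Models are run per DAP, and section 9.3.3 lists calendar time, comorbidities and care use as covariables. These can remove indirect association with receipt, but not the factor's own link.

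**The sequelae contrast.** A reader might infer that it is biased in the same way. It is not. There vaccination is the exposure, and comorbidity is an ordinary confounder that can be adjusted for.

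**Past-exposed cases are an imperfect comparator.** This stands. Their onset is later, their infection history differs, and some may be late vaccine-related cases. People given more doses also contribute more recent windows, so uptake of later doses still selects. Nothing in the documents shows that recent versus past exposure must be the main contrast.

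**Chart review.** Section 9.2.2 sends all cases following Moderna vaccination for review. Section 9.3.2, for the case-cohort, mentions review only for codes within 30 days of exposure. Under section 9.2.3 unreviewed cases cannot enter the primary analyses. If review stops at 30 days, adding past-exposed cases to the adjudicated set would not be free.

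**Conclusion.** The point holds in limited form. Section 9.7.2 does not say where past-exposed cases belong in the comparison that answers the risk-factor part of secondary objective 1. If recently exposed cases are compared with never-Moderna cases, each factor's odds ratio carries its association with Moderna receipt. That is an algebraic identity. Its size is not known from the documents: under the assumed prevalences, odds ratios of 1.42 to 2.25 arise with no true difference, and a true twofold difference can appear as 0.89. False significance is much less frequent at 20 cases per group (8-19%) than at 80 (17-58%). The amendment is worth making, because the objective is stated and the class that could serve as a check is already defined. The point does not invalidate the sequelae analysis or primary objective 1.

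**What to change.** In section 9.7.2, with matching text in the Abstract:

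1. State whether past-exposed cases count as vaccine-associated, as comparator, or as a separate group, for clinical course and for risk factors.
2. Add recently exposed versus past-exposed Moderna cases as a supportive contrast for the risk-factor part of secondary objective 1, adjusted for calendar period of onset and dose number. Use adjudicated cases if section 9.2.2 governs. Otherwise use the all-cases sensitivity set in section 9.7.5. Reconcile section 9.2.2 with section 9.3.2 on which cases are reviewed.
3. Report the risk-factor part of recent versus never-Moderna as a comparison of case mix, not as evidence that risk factors differ.

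Report both contrasts with their limits; neither need be designated the main one. The cost is protocol and SAP wording and one further model per DAP. The all-cases route needs no additional chart review, but its cases are partly unvalidated.
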